#### 4.9 Pharmacokinetic Evaluations

All PK analyses will be conducted using the treated population.

A PK sample will be collected at baseline, weeks 4, 8, 12, 24 and 48 of the Randomization Phase. Additionally, PK samples should be drawn if there are any SAEs that could possibly be drug related or severe AEs that could be drug related. Date and time of doses on the day of visits and day prior will be collected in the case report forms along with the time of last meal.

Participants who are able to schedule a morning visit for baseline, weeks 2, 4, 8, 12, 24 and 48 can be instructed to hold their dose of study drug that morning until after a PK trough sample is obtained, if possible and appropriate.

Individual concentrations will be summarized by visit for the Randomization Phase. Plasma concentrations below the limit of quantification (BQL) will be considered to be 0 concentration. Missing values will not be imputed.

Individual plasma concentration data will be displayed in listings for the Randomization Phase.

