Rationale	BHV-4157 is a new chemical entity 3rd-generation prodrug of the glutamate modulator, riluzole, which has been designed to bypass first-pass metabolism therein providing greater bioavailability, diminished PK variability, lower hepatic burden, lack of food effect, longer half-life and once daily dosing. Preclinical models suggest that riluzole, the active metabolite of BHV-4157, may protect from AD-related pathology and cognitive dysfunction.
Target Population	Male and females, age 50 to 85 years (inclusive at screening), diagnosed with Alzheimer's Disease (in accordance with NIA/Alzheimer's Association Guidelines) of mild to moderate severity including MMSE score 14-24 at the screening visit.
	Eligible participants should be receiving a stable dose of FDA-approved AD medication(s) (acetylcholinesterase inhibitors (AchEI) and/or memantine) for at least 3 months prior to screening and willing to remain on same dose(s) for trial duration. Those participants with contraindications or failed treatment with either AchEI and/or memantine will be eligible for inclusion.
Number of Participants	Approximately 336 participants will be randomly allocated using a 1:1 allocation to active treatment or placebo.
Drug Dosage & Treatment Duration	Titrated dose of BHV-4157 to 280 mg, or placebo, taken orally once daily. Duration of double-blind treatment is approximately 48 weeks. There is also a screening period of up to 42 days; and a 4-week post-treatment observation period. Eligible subjects will have the opportunity to continue in a 48-week openlabel extension phase (once it is open for recruitment at their investigative site).
Objectives	Randomized Double-Blind Treatment Phase
	The co-primary objectives are to: evaluate the efficacy of BHV-4157 as measured by a) ADAS-Cog 11, and b) CDR-Sum of Boxes.
	The secondary objectives are to: (1) evaluate the efficacy of BHV-4157 as measured by: volumetric MRI (Quarc bilateral hippocampal volume)

Neuropsychiatric Inventory (NPI), ADCS-ADL, and Mini-Mental State Examination (MMSE). (2) evaluate the safety and tolerability of BHV-4157 as measured by mortality rates, serious adverse events, adverse events, clinical safety laboratories, physical examinations and significant ECG changes.

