3.3 Exploratory Objectives

Exploratory objectives are to assess:

- Efficacy of BHV-4157 assessed by the Montreal Cognitive Assessment (MoCA)
- Evaluate the efficacy of BHV-4157 on performance using the AD Composite Score (ADCOMS)
- Volumetric MRI (bilateral lateral ventricles and whole brain volume)

- A cognitive composite outcome computed using measures from the NACC Neuropsychological Test Battery [Craft Story 21 Recall (Immediate & Delayed); Benson Complex Figure (Copy & Delayed Recall); Multilingual Naming Test; Letter & Category Fluency; Trail Making Test A & B; Number Span Forward and Backward]
- Pharmacokinetics of BHV-4157 and riluzole in plasma
- Treatment response by Apo E genotype
- CSF, serum and plasma biomarkers (AB42, AB42/40 ratio, total tau, p-tau-181, neurogranin, NfL, YKL-40, VILIP, SNAP-25, sTREM2, GFAP) at screening, week 24 and week 48 of the double-blind phase. CSF will be assessed in a subset of the study population (estimated n=50 active, n=50 placebo)

3.3.1 Exploratory Open-Label Extension Phase Objective

Exploratory Open-Label Extension Phase objective is to evaluate the safety and tolerability of BHV-4157 as measured by mortality rates, serious adverse events, adverse events, clinical safety laboratories, physical examinations and significant ECG changes.

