8.3 Pharmacokinetic Assessments

A plasma sample for pharmacokinetic (PK) should be collected at baseline, week 4, week 8, week 12, week 24, and week 48 of the double-blind phase of the trial. Participants should take their dose at their routine time on the days of these visits. Date and time of last dose should be collected in case report forms for entry into the EDC system. Participants who are able to be scheduled for a morning visit should be instructed to hold their dose of study drug that morning until after a PK trough sample is obtained, if possible and appropriate in the judgment of the investigator.

PK samples should be drawn if there are any SAEs that could possibly be drug-related or severe AEs that could be drug-related.

In addition, for participants undergoing lumbar puncture, plasma samples for PK should be drawn at the time of lumbar puncture for Week 24 and Week 48 visits for the double blind placebo phase. Date and time of last dose should be collected in case report forms for entry into the EDC system.

There is no PK sampling during the OLE phase.

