10 EARLY DISCONTINUATION/WITHDRAWAL PROCEDURES

The entire study may be discontinued at the discretion of ADCS or Biohaven. In these circumstances the Investigator will arrange for all ongoing participants to be seen and for their study medication to be discontinued as soon as is safely possible.

Participants are free to withdraw from study participation at any time, for any reason, and without prejudice.

Discontinuation of study treatment and/or the participation of an individual participant in the study will be terminated in the following circumstances:

- Withdrawal of informed consent by the participant or LAR. If the study partner withdraws
 his/her consent to participate then attempts will be made to find a replacement. In any event
 the participant will be continued in the study in so far as possible. Participants who
 withdraw consent will be advised by the Investigator regarding subsequent treatment and
 investigation.
- Treatment of a participant with a non-permitted concomitant medication may necessitate discontinuation from study medications, and will be determined by the Investigator in conjunction with the Medical Monitor.
- Adverse event or other significant medical condition which, in the opinion of the Investigator render it necessary to discontinue study medication.
- The participant experiences a medical emergency that necessitates unblinding their treatment assignment. (See Section 6.6).
- Any other occurrence that, in the Investigator's opinion, makes continued participation contrary to the participant's best interests.
- Movement of participant into a long-term care nursing facility. Movement into an assisted living facility is not cause for discontinuation from the study.

Participants who discontinue active treatment for any reason will have the opportunity to continue on the protocol with further visits per protocol to the end of the double-blind phase of the study with their ongoing consent. Their continued participation will be encouraged.

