#### 4.10.1 Extent of Exposure and Compliance to Study Treatment

Participants will receive placebo (QD) or BHV-4157 (140 mg QD followed by 140 mg BID) during the Randomization Phase. For the Extension Phase subjects will receive open label BHV-4157 (140 mg QD followed by 140 mg BID).

For the Randomization Phase, the extent of participant exposure (including missed dose days) will be quantified as the number of days on study drug (placebo or BHV-4157) and measured from the time the participant received the first dose until the time the participant received the last dose (i.e., total days on randomized study medication = last day of double-blind randomized study medication – day 1 of double blind randomized study medication + 1).

For the Extension Phase, the extent of participant exposure (including missed dose days) will be quantified as the number of days on study drug (open label BHV-4157) and measured from the time the participant received the first dose in the Extension Phase until the time the participant received the last dose (i.e., total days on open label medication = last day of open label study medication – day 1 of open label study medication + 1).

For combined exposure of BHV-4157 either the randomization and the extension phase, the extent of participant exposure (including missed dose days) will be quantified as the number of days on study drug (BHV-4157) and measured from the time the participant received the first dose BHV-4157 until the time the participant received the last dose of BHV-4157 regardless of phase (i.e., total days on randomized study medication = last day of BHV-4157 study medication – day 1 of BHV-4157 study medication + 1).

Extent of participant exposure for a given phase or overall for BHV4157 will also be calculated only including days where number of capsules taken was >0 (total days on study medication).

For the Randomization Phase, the number of participants on-treatment and their average daily dose (including minimum and maximum) will be summarized by 14-day intervals for the first 28 days and then by month (28-day intervals) as well as overall for the randomization phase. For participants on placebo the number of capsules will be summarized.

For the Randomization Phase, the extent of study medication exposure will also be summarized by a Kaplan-Meier plot presenting proportion of participants still on Randomization Phase study medication (including days of missed dose).

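### SAP 4.9 summarises PK concentrations by visit without separating pre-dose troughs from post-dose samples, although Protocol 8.3 produces both at the same visit

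*SAP*

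**What the plan says.** **Objective.** Protocol 3.3 lists "Pharmacokinetics of BHV-4157 and riluzole in plasma" among the exploratory objectives, and Protocol 12.5 leaves the analysis of exploratory endpoints to the SAP.

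**Sampling.** Under Protocol 8.3, plasma is drawn at baseline and Weeks 4, 8, 12, 24 and 48. The default is that "Participants should take their dose at their routine time on the days of these visits". Those who can come in the morning are told to "hold their dose of study drug that morning until after a PK trough sample is obtained", if possible and appropriate. Further PK samples are taken at lumbar puncture (Weeks 24 and 48) and after certain adverse events. The timing of recent doses goes into the case report form (Protocol 8.3, SAP 4.9).

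**Analysis.** SAP 4.9 uses the treated population and states "Individual concentrations will be summarized by visit for the Randomization Phase". It also plans listings of individual values. For low values, "Plasma concentrations below the limit of quantification (BQL) will be considered to be 0 concentration". It names no category for time since dose, no split by dose taken and no on-treatment condition.

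**Continued visits.** Protocol 10 says "Participants who discontinue active treatment for any reason will have the opportunity to continue on the protocol with further visits per protocol". The Week 48 or Early Termination visit (Protocol 8.1.9) includes a PK sample.

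**Dosing frequency.** The protocol summary describes study drug as "taken orally once daily". SAP 4.10.1 gives the active regimen as "BHV-4157 (140 mg QD followed by 140 mg BID".

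**The concern.** A concentration is interpretable only against the time since the last dose. Two participants at the same nominal visit, one sampled before the dose and one a couple of hours after it, contribute different quantities. A summary across both is neither trough nor post-dose exposure, and its value depends on how many attended in the morning and held the dose.

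A reader of the Week 4 to Week 48 table would naturally take a rise as accumulation and a fall as loss of exposure or adherence. Either could come from the appointment mix alone. Samples from participants who have stopped drug but still attend would pull the summary down for a reason unrelated to the drug's disposition. This table is the only PK summary the SAP plans.

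**Working it through.** The documents give no concentration, half-life or PK sample size, so there is no figure to reproduce. The check has three parts.

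**1. Does the plan separate the sample types anywhere?** Protocol 8.3 creates two types within a visit. SAP 4.9 groups by visit. SAP 4.3.1.2 adds randomized group as the default for tabulations, and Protocol 6.6 aims to avoid assaying placebo samples needlessly, so the table is in effect by visit within the active arm. No passage adds time since dose, although it can be derived from the recorded dose times.

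**2. How far could the sampling mix move the mean?** Assumed inputs, none from the documents:
- mono-exponential decline at steady state, half-life *h* of 6, 12 or 24 h;
- every non-trough sample taken 2 h after dose;
- trough at 24 h or 12 h, because the once-daily and BID passages leave both open;
- share of troughs *p* falling from 0.7 at one visit to 0.3 at another.

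Ratio of post-dose to trough: R = 2^((T − 2)/h), with T = 24 or 12. Mean relative to trough: p + (1 − p)R.

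| Trough time T | h | R | Mean at p = 0.7 | Mean at p = 0.3 | Apparent rise |
|---|---|---|---|---|---|
| 24 h | 6 h | 2^(22/6) = 12.70 | 4.51 | 9.19 | 104% |
| 24 h | 12 h | 2^(22/12) = 3.56 | 1.77 | 2.79 | 58% |
| 24 h | 24 h | 2^(22/24) = 1.89 | 1.27 | 1.62 | 28% |
| 12 h | 6 h | 2^(10/6) = 3.17 | 1.65 | 2.52 | 53% |
| 12 h | 12 h | 2^(10/12) = 1.78 | 1.23 | 1.55 | 25% |
| 12 h | 24 h | 2^(10/24) = 1.33 | 1.10 | 1.23 | 12% |

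A smaller shift, from 0.6 to 0.4, gives (0.4 + 0.6R)/(0.6 + 0.4R) − 1. That is 41%, 25% and 13% for the 24-hour trough, and 23%, 12% and 6% for the 12-hour trough. With no shift at all and p = 0.5, the mean is (1 + R)/2 times the trough: from 1.17 (T = 12, h = 24) to 6.85 (T = 24, h = 6). So the level is hard to read even when the mix is stable.

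**3. Off-drug samples and dose level.**
- The sections on laboratory data, vital signs and ECG (SAP 4.10.3, 4.10.5, 4.10.6) each state an on-treatment limit. SAP 4.9 does not.
- SAP Table 3 places PK with the safety parameters. If the safety period in SAP 4.4 carries over, it ends 30 days after the last dose, which is 30 once-daily intervals. At the longest assumed half-life (24 h), a sample 7 days after the last dose is at (1/2)^7 = 0.8% of its starting level. If that is BQL it enters as 0. Each 10% of zeros multiplies the mean by 0.9.
- The first scheduled post-dose sample is Week 4, after the Week 2 escalation call. Samples at 140 mg therefore come from participants who did not escalate or were reduced, or from event-driven draws in the Day 2–42 window. Their number is unknown. If 10% were at 140 mg with dose-proportional levels and 10% were zeros, an all-trough mean would be (0.9 + 0.1 × 0.5) × 0.9 = 0.855 of the 280 mg trough.
- Under Table 3 the latest record in a window is used. A lumbar-puncture or event-driven sample can therefore replace the scheduled one by date, whatever its type.

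**The case against.** The SAP promises more than a mean by visit. Tables are by randomized group by default, and the standard set includes n, median, SD, minimum and maximum. Individual values are listed and dose times are collected, so time since dose can be derived at any stage. All of this stands, and a reader who inferred that PK is only averaged by visit, or that the data cannot describe pharmacokinetics, would go too far. It does not repair the planned table. The median and range come from the same mixture; in the two-point illustration the median switches from the trough value to the post-dose value as *p* falls from 0.7 to 0.3.

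A reader might also infer that off-drug participants are set to zero by rule. The rule concerns BQL results, not drug status. Zeros for off-drug samples are an inference, and the 30-day limit may remove the later ones. Nor do the documents show a material number of 140 mg samples. The overdose definition in Protocol 11.4, which mentions both doses, could simply reflect titration.

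The size is the weakest part. Half-life, the 2-hour sampling time and the shift in trough share are all assumed. The same hold instruction applies at every visit, and nothing in the documents predicts a 70%-to-30% change. The percentages show sensitivity, not expected bias.

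**Conclusion.** The point holds for time since dose. Followed exactly, SAP 4.9 pools held-dose troughs with post-dose samples taken at uncontrolled times, and the resulting summary cannot be read as either. This conclusion rests on the text alone.

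The size is illustrative: for the 70%-to-30% shift, an apparent rise of 28% to 104% with a 24-hour trough and 12% to 53% with a 12-hour trough, under the assumptions above. Timing is likely to be the dominant issue. Off-drug samples are a smaller gap, because their exclusion is unclear and not because they are certainly included. The 140 mg contribution is unknown and may be small.

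PK is exploratory and carries no hypothesis test. Primary, secondary and safety conclusions are not affected. The change is worth making but is not critical.

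**What to change.** Amend SAP 4.9 before unblinding, so that the grouping is not chosen after the data are seen:

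- For the active arm, summarise BHV-4157 and riluzole separately, by visit and by pre-dose trough versus post-dose time-since-dose category, derived from the recorded dose times. Make trough by visit the main table.
- Show the dose actually taken where more than one occurs at a visit.
- List samples taken after drug discontinuation, but leave them out of the summaries.
- State that lumbar-puncture and event-driven samples do not replace the scheduled visit sample under the latest-record rule.
- Reconcile the protocol's once-daily passage with the BID passage in SAP 4.10.1 before defining the trough category. Also reconcile the mention of Week 2 among the trough visits in SAP 4.9 with the schedule, which has only a telephone call then.

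The cost is wording, some extra programming and smaller cells. No new samples or data fields are needed. If cells become too small, a simple pre-dose versus post-dose split would still remove the main ambiguity.

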#### 4.10 Safety and Other Analyses

Safety and other exploratory analyses will be conducted on the Treated Participants Population for the respective phase. Separate summaries will be provide for Randomization and Extension

Phases. In addition, where indicated safety summaries for the combined all BHV-4157 exposure will be provided.

Safety outcome measures include: AEs, laboratory assessments, physical examinations, vital signs, ECGs, concomitant medications, and the S-STS questionnaire.

Continuous values will be summarized by descriptive statistics (mean, median, SD, minimum, maximum, and number of participants). Mean line plots over time may be displayed if applicable with separate lines for each treatment.

Categorical variables will be summarized using the number and percentage of participants in each category for each treatment group and overall. The denominators for calculating the percentages will be based on the number of participants with non-missing assessments at a particular visit for the safety population.

In order to assess the impact of the COVID-19 pandemic crisis on safety results, select safety summaries will be repeated separating subjects by whether they were active (on-treatment) in the double-blind Randomization phase on or after March 13, 2020 or only active prior to this date.

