#### 4.3.5 Subpopulations

The subgroups of interest for this study are:

- Sex
- APOE (e4 vs no or missing)
- Mild vs moderate (mild AD:MMSE 20 to 24; moderate AD: MMSE 14 to 19)
- Participation during Covid-19 (opportunity to complete randomization phase before March 13, 2020 vs on or after March 13, 2020)

Except where indicated otherwise, descriptive summaries will be provided for the co-primary endpoints for each subgroup.

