#### 4.7 Demographic and Baseline Characteristics

Tabulations of demographic and baseline characteristics, including age, sex, racial group, smoking habits, level of education, disease and medical history, and current standard of care treatment, will be made for all treated participants. A separate set of tabulations will be made for participants enrolled but not randomized. Demographic information will be summarized by treatment group and for all treatment groups combined.

In addition to all Treated subjects additional summaries will be provided for:

- Subjects completing or discontinuing the double-blind randomization phase before March 13, 2020 (the reference date for the start of the COVID-19 pandemic based on the date National Emergency declared)
- Subjects still active in the double-blind randomization phase on or after March 13, 2020

Demographic and other baseline data will also be provided in by-participant data listings.

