For the Extension Phase and the entire study, the number of subjects on-treatment and their average daily dose (including minimum and maximum) will be summarized by month (30-day intervals) for the as well as overall for the Extension Phase and the entire study (BHV-4157 exposure).

Additionally, percent (%) compliance will be calculated and summarized as follows:

- Randomization Phase % compliance = total days on study medication (i.e. number of days where number of capsules taken > 0) during the Randomization Phase / (last dose date in Randomization Phase– first dose date + 1) × 100
- Extension Phase % compliance = total days on BHV-4157 in Extension Phase / (last dose date first dose date in Extension Phase + 1) × 100
- Overall % compliance = total days on BHV-4157 during the study / [(last BHV-4157 dose date first BHV-4157 dose date + 1) (number of days with a dosing break in dosing between the Randomization and Extension Phases)]

Summaries on the Randomization Phase will be repeated for Treated subjects completing (or discontinuing) double-blind treatment prior to versus on or after start of COVID-19 pandemic crisis (March 13, 2020).

Study drug administration and compliance will be listed in participant data listings.

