An evaluation of drug-induced serious hepatotoxicity (eDISH) scatter plot will display the maximum TBL ratio of value to ULN on the y-axis versus the maximum ALT ratio of value to ULN on the x-axis, where the maxima is not necessarily concurrent, for treated subjects in the randomization phase and DB and OL BHV-4157 treated subjects. Both axes will be on the log10 scale. Ratios < 0.1 x ULN will be set to 0.1. Sample sizes in the legend will represent subjects with paired ratios. A horizontal reference line will be placed at 2 x ULN, and a vertical reference line will be placed at 3 x ULN. The lower left quadrant will be labeled "Normal Range", the upper left quadrant will be labeled "Hyperbilirubinemia", the lower right quadrant will be labeled "Possible Hy's Law Range."

All laboratory data will be presented in data listings. Additional listings will be presented for all abnormal laboratory values considered potentially clinically significant (Grade 3 or 4) for the Randomization and Extension Phases. Participants with a maximum value of ALT or AST >3x ULN or a maximum total bilirubin value >2x ULN observed at any point during the entire study will also be presented in a listing. Note that these abnormalities do not need to occur on concurrent visits.

The following summary for the Randomization Phase will be repeated for Treated subjects completing (or discontinuing) double-blind treatment prior to versus on or after start of COVID-19 pandemic crisis (March 13, 2020):

The number and percent of subjects with at least one on-treatment lab assessment by highest grade will be summarized for each treatment (regardless of baseline) for the Randomization Phase

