#### 4.10.5 Vital Signs and Physical Measurements

The observed value and change from baseline in vital signs and physical measurements will be summarized for each arm at each visit for the Randomization and Extension Phases, separately. The summary will be based on the "on-treatment" data after the date/time of first dose of study drug and within 30 days after the last dose of study drug (see section 4.3 for detailed definition of "on-treatment").

In addition, the number and percentage of participants with at least one post-treatment vital sign measurement meeting any of these criteria will be summarized:

- Systolic Blood Pressure: <90 mmHg, >140 mmHg, >160 mmHg
- Diastolic Blood Pressure: <50 mmHg, >90 mmHg, >100 mmHg
- Pulse Rate: <60 bpm, >100 bpm
- Body Weight: decrease of  $\geq$ 7% from baseline and increase of  $\geq$ 7% from baseline
- Temperature: >38.0 °C, <36.0 °C

The number and percent of subjects meeting these criteria will be summarized for the Randomization and Extension Phase, separately as well as the overall BHV-4157 treated exposure. A subject listing will provide for each vital sign measure abnormality criteria listing any subject meeting the criteria with a complete list of all of their values that particular vital sign measure with the specific assessments that meet the criteria indicated.

The criteria summarized for the Randomization Phase will also be repeated for Treated subjects completing (or discontinuing) double-blind treatment prior to versus on or after start of COVID-19 pandemic crisis (March 13, 2020).

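### The COVID-19 safety repeats group participants by when they actually stopped drug, so the repeated exposure and Kaplan-Meier summaries differ between groups even if the pandemic had no effect

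*SAP*

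**What the plan says.** SAP 4.10 gives the purpose, which is to assess how the pandemic affected the safety results, and plans to repeat select summaries "separating subjects by whether they were active (on-treatment) in the double-blind Randomization phase on or after March 13, 2020" or active only before it.

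The later subsections apply the rule:

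- 4.10.1 (exposure and compliance) repeats the Randomization Phase summaries for "Treated subjects completing (or discontinuing) double-blind treatment prior to versus on or after start of COVID-19 pandemic crisis". These include days on drug, percent compliance and a Kaplan-Meier plot of the proportion still on medication.
- 4.10.3 repeats the highest-laboratory-grade table for participants "completing (or discontinuing) double-blind treatment prior to versus on or after start of COVID-19 pandemic crisis".
- 4.10.5 says: "The criteria summarized for the Randomization Phase will also be repeated for Treated subjects completing (or discontinuing) double-blind treatment" before versus on or after the date. 4.10.6 does the same for the ECG criteria.
- 4.7 adds baseline tables on the same kind of split, beginning with "Subjects completing or discontinuing the double-blind randomization phase before March 13, 2020".

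For the co-primary endpoints, SAP 4.3.5 and the subgroup list in 4.8.3 define the COVID-19 subgroup as "opportunity to complete randomization phase before March 13, 2020 vs on or after March 13, 2020". Early stopping does not change membership of that subgroup. Nothing in the SAP corrects the safety split for early discontinuation or unequal time on drug.

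**The concern.** Stopping drug is a post-randomisation outcome and part of what the safety tables describe. Take two participants randomised on the same day in 2019, both due to finish after 13 March 2020. The one who stops in February goes to the earlier group and the one who continues goes to the later group. Everyone in the later group has, by selection, stayed on drug to the cut.

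Total exposure and the Kaplan-Meier curve must then look better in the later group, whatever the pandemic did. A reader using these tables for the purpose stated in 4.10 could take the gap for a pandemic effect. A real effect could also be hidden in it: Protocol 8.1.9 allows treatment of up to 60 weeks when the Week 48 visit is delayed, which lengthens exposure in the same direction as the artefact. If one arm loses more participants early, the arms within each group also stop being comparable.

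**Working it through.** **Inputs.** From the SAP: 48 weeks (336 days) of treatment (2.1); 336 participants and at most 26% dropout (4.2); cut date 13 March 2020. Assumed: 26% is the proportion stopping drug by day 336 (the SAP states it as study dropout); uniform accrual ending before the cut, because the documents give no enrolment calendar; and no pandemic effect of any kind.

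**The plan's own figure.** 336 × 0.74 = 248.6, which the SAP gives as 248, or 124 per arm. This reproduces.

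**Opportunity-to-complete split.** With a constant hazard, λ = −ln(0.74)/336 = 0.000896 per day. Mean exposure is (1 − 0.74)/λ = 0.26/0.000896 ≈ 290 days = 41.4 weeks. It does not depend on entry date, so both groups have 41.4 weeks.

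**Stop-date split, base case (accrual 1 August 2018 to 15 December 2019, 501 days).**

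1. Participants entering before 12 April 2019 (cut minus 336 days) are due to finish before the cut: 254/501 × 336 = 170.3. The other 165.7 are due on or after it.
2. Those 165.7 entered 89 to 336 days before the cut. Their average probability of still being on drug at the cut is (e^(−89λ) − e^(−336λ))/(247λ) = (0.923 − 0.740)/0.221 = 0.828.
3. The later group is 165.7 × 0.828 = 137.2. The remaining 28.5 (17%) move to the earlier group only because they stopped, making it 198.8.
4. A later-group member who entered u days before the cut has expected exposure u + (1 − e^(−λ(336−u)))/λ. Weighted by e^(−λu) and averaged over u from 89 to 336, this gives 46.7 weeks.
5. By balance, the earlier group has (336 × 41.45 − 137.2 × 46.70)/198.8 = 37.8 weeks.

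In this scenario the later group's Kaplan-Meier curve stays at 100% for at least 89 days by construction.

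**Sensitivity: mean weeks on drug, earlier / later group.**

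| Assumed accrual | Constant hazard | Front-loaded stopping (Weibull shape 0.6) |
|---|---|---|
| 1 Jul 2018 – 30 Jun 2019 | 40.2 / 47.9 | 38.3 / 47.9 |
| 1 Jul 2018 – 31 Oct 2019 | 38.6 / 47.1 | 36.3 / 47.4 |
| 1 Aug 2018 – 15 Dec 2019 | 37.8 / 46.7 | 35.2 / 47.0 |
| 1 Sep 2018 – 1 Feb 2020 | 37.1 / 46.2 | 34.1 / 46.5 |
| Opportunity split, any calendar | 41.4 / 41.4 | 39.9 / 39.9 |

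For accrual starting 70-95 and ending 8-20 weeks before the cut, constant hazard gives about 36-39 / 46-47. With 10% stopping instead of 26%, the base case is 43.9 / 47.5, against 45.6 in both groups under the opportunity split. Extending on-treatment status to last dose + 30 days leaves the gap: 37.2 / 46.4.

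**At-least-one tables.** Assume a laboratory abnormality at 15% per 48 weeks (base-case accrual, constant hazard).

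- Unrelated to stopping: 11.9% ever abnormal in the earlier group and 14.6% in the later, although the rate per 48 weeks on drug is equal (0.15 in both).
- Half of the events lead to stopping: the order reverses, 14.6% and 10.5%. The rates per 48 weeks are now 0.195 and 0.108, so dividing by exposure while keeping the stop-date groups does not cure the problem.

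**Tables not mechanically affected.** Percent compliance divides days taken by days from first to last dose, so early stopping does not lower it. The baseline tables only describe who is in each group.

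**The case against.** The strongest reply is that safety in this SAP is an on-treatment question (4.4), whereas the primary efficacy estimand follows a treatment-policy strategy (4.3.1.1). On that view, who was on drug during the pandemic is a natural grouping, and a definition different from the efficacy one is not in itself an error. The opportunity split also has its own misfit: someone who stopped in February 2020 but was due to finish later enters the later group with no on-drug time in the pandemic. Both points stand. They support the current rule as a description of who was exposed. They do not make the earlier group a valid comparator, and they are the reason for a calendar-time split of event-type tables.

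Three stronger readings are tempting, and the documents do not support them.

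- *A false pandemic effect will appear in adverse-event discontinuation.* No AE table is named among the repeats. SAP 4.10.2 only flags pandemic status in listings, and 4.6 reports COVID-related discontinuation from a dedicated form.
- *The laboratory, vital-sign and ECG percentages are biased in a known direction.* The example above reverses under a plausible change of assumption.
- *The trial's conclusions are at risk.* The repeats are descriptive. The main safety summaries on all Treated Participants, the co-primary analyses and the type I error rate do not use this split.

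**Conclusion.** The point holds for a limited set of descriptive tables. The repeated total-exposure and Kaplan-Meier summaries in 4.10.1 cannot serve the purpose stated in 4.10: with no pandemic effect they differ by roughly 7 to 11 weeks of mean exposure (36-39 versus 46-47), and by about 8 to 12 weeks over the tabulated calendars and stopping patterns. The size rests on assumed accrual and on reading 26% as stopping drug. The direction was the same in every scenario tried and follows from the selection itself. The at-least-one laboratory, vital-sign and ECG percentages are not comparable between groups, with no fixed direction. Percent compliance and the baseline tables are not mechanically biased.

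A separate wording fault remains. SAP 4.10 groups by on-treatment status, which 4.4 extends to 30 days after the last dose (or to the first extension dose, if earlier). Sections 4.10.1 to 4.10.6 group by the date of completing or discontinuing. These are two different rules.

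**What to change.** 1. **Exposure and Kaplan-Meier repeats (4.10.1):** use the opportunity-to-complete definition of 4.3.5. State its formula, which the SAP does not give, for example planned Day 336 before versus on or after 13 March 2020.
2. **Laboratory, vital-sign and ECG repeats (4.10.3, 4.10.5, 4.10.6):** split on-treatment person-time and events, not participants, at 13 March 2020 and report exposure-adjusted rates by arm for each period.
3. **Wording:** reconcile the on-treatment rule in 4.10 and 4.4 with the stop-date rule in 4.10.1 to 4.10.6.

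The baseline tables in 4.7 may stay if labelled as a description of who was still active.

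**Cost and limits.** SAP wording and some extra programming, with no new data. The later group under item 1 will include some people with no on-drug time in the pandemic, which a footnote should say. Under item 2, person-time after the cut tends to come later in treatment. Protocol 1.7.1.3 reports that ALT rises on riluzole usually peak within 3 months of starting, so a lower rate after the cut should be read beside time on drug.
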